10.3 Demographic and Baseline Parameters

Demographic and baseline parameters will be summarized. All continuous variables will be summarized by descriptive statistics. All discrete variables will be summarized by frequencies and percentages.

10.4 Safety Analysis

Analysis for the safety endpoint will be descriptive in nature.

AEs will be coded by the MedDRA (version 18.0 or later) system organ class and preferred term. AE data will be listed individually and summarized by system organ class and preferred terms within a system organ class for each indication. In addition, summary of AEs will be presented by severity and relation to study treatment.

Serious adverse events will be similarly summarized.

10.5 Efficacy Analysis

1) Clinical success – Diagnostic yield

For both MCC-T and EGD, we will be assessing rates of diagnosis of clinically relevant pathology in patients with upper abdominal pain. Detection of D2 findings will be considered positive. Sensitivity, specificity, positive predictive value, and negative predictive values will be calculated for both MCC-T and EGD. In this study the “gold standard” will be the expert group’s decision regarding the presence of a relevant finding. McNemar’s test will be used to assess for statistically significant differences between the two modalities. Sub-analyses will be performed to compare accuracies of the two modalities based on anatomic region (i.e. esophagus, stomach, duodenum) and across various lesions (i.e. ulcers, gastropathy, esophagitis, etc.).

2) Secondary Outcomes

Technical success:

- i. We will assess the ability of the -MCC-T and the EGD to photo document the esophagus, stomach, and duodenum as described in this protocol.
- ii. We will assess the ability of the MCC-T to be released upon command in the stomach once esophageal examination is complete.

Learning curves:

When training staff to use the device, we will assess how many capsules it takes to obtain “competency.” This will be defined as being able to obtain the appropriate photo documentation as described above at a 90% success level.

Patient satisfaction

Patient responses will be analyzed on a Likert scale to determine which procedure did the patients prefer.

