4.2 Study Endpoints

Primary

Effectiveness:

For both MCC, MCC-T and EGD, rates of diagnosis of clinically relevant pathology in patients with upper abdominal pain will be assessed. Detection of D2 findings will be considered positive. Sensitivity, specificity, positive predictive value, and negative predictive values will be calculated for both MCC and EGD. In this study the “gold standard” will be the expert group’s decision regarding the presence of an abnormal finding. McNemar’s test will be used to assess for statistically significant differences between the two modalities. Sub-analyses will be performed to compare accuracies of the two modalities based on anatomic region (i.e. esophagus, stomach, duodenum) and across various lesions (i.e. ulcers, gastropathy, esophagitis, etc.).

Safety: Rate of device or procedure related adverse events during the procedures or in the follow-up period (24 hrs. post procedure).

Secondary

Examination completion: Compare rates of complete examination of the foregut by MCC or MCC-T and EGD in patients presenting with upper abdominal complaints using sets of predetermined still images

Patient Satisfaction: Assess patient satisfaction for patients undergoing MCC or MCC-T and EGD.

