10.1 Statistical Methods

All data collected will be summarized and presented. Continuous variables will be described as the mean, median, standard deviation, and range of n observations. Categorical data will be described with contingency tables including frequency and percentage. Individual patient listings of all data will be generated and presented. Sensitivity, specificity positive predictive value and negative predictive value will be calculated using EGD as the gold standard. Comparison between readers will be measured by a Kappa statistic. Statistical tests will be performed at the University of Massachusetts Medical School. Statistical descriptions and analyses will be carried out using STATA version 13.

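### Section 10.1 scores the primary accuracy measures against EGD, while 10.5, 4.2 and the synopsis score capsule and EGD against the expert group; under 10.1, EGD is 100% accurate by construction

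*Combined protocol and SAP*

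**What the plan says.** Section 10.5 (Efficacy Analysis), under an item on diagnostic yield, counts a D2 finding as a positive: "Detection of D2 findings will be considered positive". It asks for four accuracy measures per modality, and the sentence that lists them ends by saying that "negative predictive values will be calculated for both MCC-T and EGD". The reference there is set by the expert group, through its "decision regarding the presence of a relevant finding". The only between-modality test named is McNemar's, in a sentence saying that this "test will be used to assess for statistically significant differences between the two modalities".

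Section 4.2 (Study Endpoints) and the synopsis give the same scheme as the primary effectiveness endpoint. Section 4.2 has "negative predictive values will be calculated for both MCC and EGD", again with the expert group as gold standard.

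Section 10.1 (Statistical Methods) names the same four measures but a different reference: "positive predictive value and negative predictive value will be calculated using EGD as the gold standard".

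Section 10.6 (Sample Size) describes a pilot of 70 patients plus up to 30 volunteers. No prevalence, accuracy rate, discordance rate, alpha or power is stated.

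**The concern.** The two rules cannot both hold for one set of primary results. Sections 10.5 and 4.2 and the synopsis treat EGD as a test that can err and ask for its accuracy alongside the capsule's. Section 10.1 makes EGD the truth. An analyst who follows 10.1 and still reports both modalities prints 100% four times for EGD, and can only count disagreements against the capsule.

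The first primary objective in 4.1 is to demonstrate the capsule's effectiveness relative to EGD in finding abnormalities. A lesion that EGD missed and the capsule found is the most informative evidence for that objective, and under 10.1 it is scored as a capsule error. Because nothing ranks the two rules, the choice could also be made after the results are seen.

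**Working it through.** The plan has no figure of its own to reproduce here. The first step needs no assumed numbers; the other two use illustrative inputs.

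**1. What follows from the definitions**

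With EGD as reference, reference-positive means EGD-positive.

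- EGD sensitivity = P(EGD+ | EGD+) = 100%. Specificity, PPV and NPV are 100% in the same way.
- A capsule-positive, EGD-negative patient is a capsule false positive, whatever the expert group decides.
- In McNemar's table for sensitivity or specificity, the cell where the capsule is right and EGD wrong is always 0. With k capsule errors the exact two-sided p is 2 × 0.5^k: k = 5 gives 0.0625 and k = 6 gives 0.031.

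**2. Shift in the capsule's own figures**

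Assumed: D2 prevalence 0.30; capsule sensitivity 0.80 and specificity 0.85; EGD 0.90 and 0.97; errors independent given true status.

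- P(EGD+) = 0.30×0.90 + 0.70×0.03 = 0.291, so P(EGD−) = 0.709
- P(capsule+) = 0.30×0.80 + 0.70×0.15 = 0.345, so P(capsule−) = 0.655
- P(both+) = 0.30×0.80×0.90 + 0.70×0.15×0.03 = 0.216 + 0.00315 = 0.21915
- P(both−) = 1 − 0.291 − 0.345 + 0.21915 = 0.58315

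| Measure | Capsule, expert reference | Capsule, EGD reference | EGD, expert reference | EGD, EGD reference |
|---|---|---|---|---|
| Sensitivity | 80% | 0.21915/0.291 = 75.3% | 90% | 100% |
| Specificity | 85% | 0.58315/0.709 = 82.2% | 97% | 100% |
| PPV | 0.240/0.345 = 69.6% | 0.21915/0.345 = 63.5% | 0.270/0.291 = 92.8% | 100% |
| NPV | 0.595/0.655 = 90.8% | 0.58315/0.655 = 89.0% | 0.679/0.709 = 95.8% | 100% |

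True findings seen only by the capsule have probability 0.30×0.80×0.10 = 0.024, or 70 × 0.024 = 1.7 expected patients. Under 10.1 all of them become false positives.

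**3. Same data, two references**

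Three assumed tables with N = 70. Cells are both positive / capsule only / EGD only / neither, first for the 28 patients positive by the expert group, then for the 42 negative. p is exact McNemar for sensitivity.

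| Table | Capsule v EGD sensitivity, expert reference | Capsule v EGD sensitivity, EGD reference |
|---|---|---|
| A: 20/2/5/1; 2/3/1/36 | 22/28 v 25/28; discordant 2 v 5; p = 0.453 | 22/28 v 28/28; discordant 0 v 6; p = 0.031 |
| B: 18/1/7/2; 2/7/1/32 | 19/28 v 25/28; discordant 1 v 7; p = 0.070 | 20/28 v 28/28; discordant 0 v 8; p = 0.008 |
| C: 20/2/6/0; 0/0/0/42 | 22/28 v 26/28; discordant 2 v 6; p = 0.289 | 20/26 v 26/26; discordant 0 v 6; p = 0.031 |

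The capsule's own sensitivity is unchanged in A (78.6%), rises in B (67.9% to 71.4%) and falls in C (78.6% to 76.9%). The size and sign of that shift depend on how the errors overlap. EGD's 100% and the one-sided discordance do not.

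The yield comparison uses no reference and does not change: p = 1.00, 1.00 and 0.289 in A, B and C.

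**4. PPV and NPV**

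In A, the capsule's PPV has denominator 27 and EGD's has 28. Only 22 patients are in both, and 11 are in just one. For those 22 the reference status is the same for both exams, so no discordant pair can occur. McNemar's test therefore has no valid table for PPV, and by the same argument none for NPV.

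**The case against.** The best defence is that 10.1 is general text and 10.5 is the specific efficacy section, so 10.5 should prevail. Section 10.1 also does not say that EGD is to be scored against itself: it can be read as capsule accuracy against EGD, the layout of the two Chinese comparative studies summarised in section 2. The 100% result appears only when 10.1's reference is joined to 10.5's requirement to report both modalities. That is right as far as it goes. But no text gives either section precedence, both name the same four measures, and even the capsule-only reading scores true capsule-only findings as errors.

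A reader might go further and infer that McNemar's test is prescribed for all four measures, so that part of the primary comparison cannot be run. The documents do not support this. The four measures are only to be calculated; a separate sentence applies McNemar's test to differences between modalities, under an item about diagnostic yield, and paired D2 detection suits that test. It is valid for yield and, with the expert reference, for sensitivity and specificity. Reporting PPV and NPV without a test would be legitimate. What stands is narrower: the plan does not say which measure the test addresses.

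The illustration also has limits. Its rates are assumed. If the reference is D2 on either exam, one reading of 6.7 with 10.5, there are no false positives under the expert rule, and specificity and PPV are 100% for both exams. Table C follows that reading. Moving to EGD as reference then takes capsule specificity from 42/42 to 42/44 (95.5%) and PPV from 22/22 to 20/22 (90.9%), so the conflict still matters.

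**Conclusion.** The concern holds as a contradiction over the gold standard for the primary accuracy measures. Two consequences of 10.1 need no assumed rates: EGD scores 100% on all four measures, and McNemar's test on sensitivity or specificity can only go against the capsule. The accuracy comparison required by the primary objective is then settled in direction beforehand. The D2 yield comparison is unaffected.

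The effect on the capsule's own estimates rests on assumptions. With independent errors and the stated inputs it is a fall of 4.7 points in sensitivity, 2.8 in specificity, 6.1 in PPV and 1.8 in NPV; where errors overlap differently it can be nil or reversed, as tables A and B show. In all three tables the sensitivity p-value crosses 0.05 when the reference changes, but these are illustrations and not forecasts for this trial.

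The absence of a named test for PPV and NPV is a minor gap in detail. It does not make the primary analysis unworkable. In a pilot with no stated power the consequences are limited, but the reference standard should be settled before analysis.

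**What to change.** - **Section 10.1:** replace EGD as the gold standard with the expert-group reference of 10.5. If capsule agreement with EGD is wanted, keep it as a secondary result under its own label, without EGD accuracy figures beside it.
- **Sections 10.5 and 4.2 and the synopsis (minor clarification):** state that McNemar's test applies to D2 yield, sensitivity and specificity. Report PPV and NPV for each modality with 95% confidence intervals, for example from a bootstrap by patient. If a test is wanted, name one for paired predictive values, such as a weighted generalised score test.

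The cost is a few sentences of plan text and a few lines of code. No new patients, visits or data are needed. The only small burden is a bootstrap or one non-default test.

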Study Rationale	
In the United States patients commonly undergo esophagogastroduodenoscopy (EGD) for upper abdominal symptoms to try to resolve whether they have gastroesophageal reflux disease or functional dyspepsia, if they are older than the age of 60 with symptoms, or have alarm symptoms such as unexplained weight loss, persistent nausea and vomiting or if they have symptoms that are refractory to acid suppression therapy. Given the increasing burden of digestive disease in the United States, the use of EGD is increasing in volume nationwide. EGD usually requires either conscious sedation or monitored anesthesia sedation, which has put an additional cost burden on the healthcare system. Since MCC or MCC-T does not require sedation, it offers an attractive option for both patients and clinicians alike.
 
The aim of this study is to compare in the same patient the accuracy of the MCC and MCC-T and EGD in patients presenting with upper abdominal symptoms.

Objectives	
Primary:
 
 1. To demonstrate the effectiveness of the MCC and MCC-T compared to EGD in identifying lesions in patients presenting with upper abdominal symptoms. 2. To evaluate rates of adverse events and overall safety of MCC and MCC-T as compared to EGD. 
Secondary:

	
 1. To compare rates of complete examination of the foregut by MCC and MCC-T and EGD in patients presenting with upper abdominal symptoms using sets of predetermined still images. 2. To assess patient satisfaction for patients undergoing MCC or MCC-T or EGD.
Study Design	Prospective, single center, tandem study.
Study Duration	
Total duration of the study for each patient will be 7-14 days including follow-up 24 hrs. after the final study related procedure.
 
Total anticipated study duration, including data analysis and final report, is estimated to be up to 12 months.

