Exclusion Criteria	
 1. Patient with dysphagia. 2. Patient with previous intestinal surgery. 3. Patient with Crohn's disease or other potential obstructive conditions, unless there is a recent CTE, MRE or patency capsule performed to exclude an obstructive lesion that may retain the capsule. 4. Female patient who is pregnant. 5. Patient with implanted medical device that would be potentially affected by magnets or radiofrequency emissions (e.g., pacemakers, implanted cardiac defibrillators). 6. COVID-19+ or with symptoms consistent with the infection. Fever, new cough, myalgias, and chills
Study Population and Sample Size	Since there is no predicate data in the USA, we plan a pilot study with 100 patients and 10 volunteers to help optimize the use of the MCC and MCC-T

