4 STUDY OBJECTIVES

4.1 Study Objectives

Primary:

1. To demonstrate the effectiveness of the MCC and MCC-T when compared to EGD in identifying esophageal, gastric and duodenal abnormalities in patients presenting with upper abdominal symptoms.
2. To evaluate rates of adverse events and overall safety of MCC-T as compared to EGD.

Secondary:

1. To compare rates of complete examination of the foregut by MCC, MCC-T and EGD in patients presenting with upper abdominal complaints using sets of predetermined still images
2. To assess patient satisfaction for patients undergoing MCC, MCC-T and EGD.

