10.6 Sample Size

Since there is no predicate data in the United States we have elected to do a pilot study involving 70 patients and up to 30 volunteers who will help the investigators optimize the technique with the MCC and MCC-T. We will allocate patients to MCC or MCC-T randomly using a randomization protocol generated by Redcap

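### The aim is to demonstrate the capsule's effectiveness against EGD, but the only planned comparison tests for a difference, with no margin or confidence interval, so a null result could be misread as comparability

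*Combined protocol and SAP*

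**What the plan says.** The synopsis gives the first primary objective as "To demonstrate the effectiveness of the MCC and MCC-T compared to EGD in identifying lesions in patients presenting with upper abdominal symptoms". Section 4.1 has "To demonstrate the effectiveness of the MCC and MCC-T when compared to EGD in identifying esophageal, gastric and duodenal abnormalities".

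The comparison is described in the synopsis endpoints, section 4.2 and section 10.5. In each, McNemar's "test will be used to assess for statistically significant differences between the two modalities". Sensitivity, specificity, PPV and NPV are also to be calculated for capsule and EGD. On what counts as a positive result, section 10.5 says "Detection of D2 findings will be considered positive".

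The plan states no null hypothesis, significance level, margin or success threshold, although the first item of 10.5 is labelled as clinical success. Neither 10.1 nor 10.5 mentions a confidence interval.

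Two inputs to any such comparison are inconsistent:

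- **Reference standard.** Section 10.5 uses the expert group's "decision regarding the presence of a relevant finding". Section 10.1 says that the accuracy measures "will be calculated using EGD as the gold standard".
- **Number of patients.** In section 10.6, "we have elected to do a pilot study involving 70 patients and up to 30 volunteers". In the synopsis, "we plan a pilot study with 100 patients and 10 volunteers". Section 5.2 gives a total of up to 100, including up to 30 volunteers.

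**The concern.** McNemar's test takes no difference as its null hypothesis. Rejecting that null shows that one modality finds more than the other. Failing to reject it shows nothing about closeness unless the study could have detected a deficit that matters. Here the test on sensitivity uses only patients with a D2 finding, and among them only those in whom the two examinations disagree. That number is likely to be small.

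If the result is null, the plan as written would yield a p-value above 0.05 and accuracy percentages without intervals. Nothing in that output would tell a reader whether the capsule could still be missing many more lesions than EGD, and nothing in the plan warns against reading it as comparability.

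**Working it through.** **Figure in the plan.** There is none to reproduce. Section 10.6 presents the study as a pilot, with no power, effect size or discordance rate.

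**Inputs.** From the documents: 70 patients (10.6) or 100 (synopsis). Assumed, because the documents are silent: two-sided 5% level; D2 prevalence 30%, range 20% to 50%; EGD sensitivity sE = 95%; capsule sensitivity sC = 80% for a 15-point deficit; misses independent given a D2 finding. D2 patients n = N × prevalence, so 70 × 0.20, 0.30, 0.50 = 14, 21, 35, and 100 × 0.30 = 30.

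**Step 1: what the test needs.** Let b be the D2 patients found by EGD only and c those found by the capsule only.

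- Exact test, all discordant pairs one way: p = 2 × (1/2)^b. A 5–0 split gives 2/32 = 0.0625; 6–0 gives 2/64 = 0.031. With 21 D2 patients, the smallest significant deficit is 6/21 = 29 points.
- Uncorrected chi-square: (b − c)²/(b + c). A 4–0 split gives 16/4 = 4.0, p = 0.046. The smallest significant deficit is 4/21 = 19 points.

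The plan does not say which version applies, so both are carried through.

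**Step 2: expected discordance.** P(EGD only) = sE(1 − sC) = 0.95 × 0.20 = 0.19. P(capsule only) = (1 − sE)sC = 0.05 × 0.80 = 0.04. Among 21 D2 patients, 21 × 0.23 = 4.8 discordant pairs are expected, fewer than the six that the exact test needs even when all go one way.

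**Step 3: power.** This sums the multinomial probabilities of all (b, c) with p ≤ 0.05.

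| Patients | D2 prevalence | D2 patients | 15-point deficit: exact | 15-point deficit: uncorrected | 35-point deficit (sC = 60%): exact | 35-point deficit: uncorrected |
|---|---|---|---|---|---|---|
| 70 | 20% | 14 | 2% | 17% | 34% | 62% |
| 70 | 30% | 21 | 11% | 30% | 68% | 80% |
| 70 | 50% | 35 | 32% | 46% | 94% | 96% |
| 100 | 30% | 30 | 25% | 40% | 88% | 93% |

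A 20-point deficit (sC = 75%) lies between: with 21 D2 patients, 22% exact and 44% uncorrected; with 30, 44% and 58%.

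**Step 4: what an interval would add.** Suppose 21 D2 patients split 3–1 against the capsule. The exact p-value is 0.63. The observed deficit is 2/21, about 10 points, and its 95% Tango score interval runs from −12 to +31 points. The p-value says no significant difference; the interval shows that a deficit of up to 31 points is not excluded.

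**Step 5: analysis set.** Read literally, 10.2 keeps only patients who swallowed the tethered capsule, while 10.6 randomises between the two versions. With 1:1 allocation (assumed), 70 patients become 35. At 30% prevalence, power for a 15-point deficit is then about 1% exact and 9% uncorrected, averaging over the random number of D2 patients.

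**The case against.** The best defence is that this is a pilot. The title says so, and the synopsis and 10.6 explain that no US data exist to plan on. Section 10.5 lists the accuracy measures before McNemar's test, so estimation is already intended and the test is not the only primary output. That stands, and it is why the matter can be repaired by wording and analysis. It does not close the gap: a pilot's useful product is an estimate with its precision, and the precision is what the plan omits, while the objective keeps confirmatory wording.

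The power figures can also be challenged. They rest on assumed prevalence and sensitivities, and the exact test is the less favourable version. Both versions and both patient numbers are therefore shown. A null result is not the likely outcome in every case: with 100 patients and 50% prevalence (50 D2 patients), power for a 20-point deficit is 75% exact and 82% uncorrected.

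Three stronger readings are tempting, and the documents do not support them:

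- A reader might infer that a non-significant result would be declared a success. No section states such a rule; the plan only leaves room for that misreading.
- A reader might infer that the test is uninformative whichever way it falls. A significant result would be evidence of inferiority or superiority. Only a null result is uninformative.
- Section 2 describes the previous capsule studies as equivalent to EGD or gastroscopy, from which a reader might infer how this trial will be reported. Section 2 does not say that equivalence was inferred from a non-significant test.

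**Conclusion.** The concern holds as a mismatch between the stated aim and the planned comparison. A test for a difference, without a margin, success criterion or interval, cannot support a claim of comparability when it is non-significant.

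The size depends on the true deficit. For 15 points, a null result is more likely than not with 70 patients across the assumed 20% to 50% prevalence: power is 2% to 32% exact and 17% to 46% uncorrected. With 100 patients at 30% prevalence, power is 25% or 40%. The mismatch itself is in the text and does not depend on these assumptions. A blanket statement that the test would miss a clearly worse capsule goes too far, because a 35-point deficit would usually be detected at 30% prevalence or above.

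This should be changed before analysis. It does not invalidate the design or the data.

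**What to change.** 1. **Settle the reference standard first.** Reconcile 10.1 with 10.5, and use the expert group's decision for the paired comparison. With EGD as reference, EGD sensitivity and specificity are 100% by definition, and the paired difference reduces to the capsule's own figure minus 100%. Reconcile the patient number (synopsis, 5.2, 10.6) and the analysis set (10.2) at the same time.
2. **In 4.2 and 10.5 (and the matching synopsis text), make the primary result an estimate.** Report the paired difference in per-patient D2 sensitivity, capsule minus EGD, and likewise in specificity, each with a 95% interval suited to small paired samples, such as the Tango score interval. Give 95% intervals, such as Wilson, for each sensitivity, specificity, PPV and NPV. Other sound small-sample intervals would also serve; the choice should be named in advance.
3. **Keep McNemar's test as supplementary**, specify the exact version and the significance level, and state that non-significance will not be read as equivalence.
4. **In 4.1 and the synopsis, replace *demonstrate* with *estimate***, in line with a pilot.

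The cost is a few lines of analysis code and a more modest claim. No extra patients, procedures or data are needed. Keeping the confirmatory wording would instead require a justified non-inferiority margin and probably a larger study. For illustration, with both sensitivities at 90%, independent misses, one-sided 2.5% level, 80% power and a 15-point margin (all assumed), n = 2 × 0.9 × 0.1 × (1.96 + 0.84)²/0.15², about 63 D2 patients, or 63/0.30 = 210 patients at 30% prevalence.
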